1.0 Objectives

1.1 *Describe the purpose, specific aims, or objectives.*

We propose to study the effect of Acthar® on recovery from cognitive relapses in multiple sclerosis (MS). Cognitive relapses are acute clinical declines in concentration, memory, working memory or increased fatigue. Cognitive relapses may also be detected by the presence on brain MRI of new active supratentorial Gad enhancing lesions. We will use well-validated, objective metrics to evaluate cognitive changes following treatment with a 5-day course of Acthar® over three months in patients showing cognitive relapses in MS. To account for the possible practice effects of cognitive testing over a three-month period, we will compare the results to a matched sample of MS patients who are clinically stable.

1.2 *State the hypotheses to be tested.*

The primary hypothesis of the study is that due to enhanced melanocortin response, Acthar will facilitate recovery from cognitive changes occurring during cognitively focused relapse, and that patients treated with Acthar will return to baseline following treatment.

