11.0 Data Management

11.1 Describe the data analysis plan, including any statistical procedures.

Data will be processed by trained research assistants blind to study hypotheses. Analysis will be conducted using SPSS 22.0. Analysis strategy will be repeated measures analysis of variance where baseline, day 0 and day 90 scores are compared. Analysis of variance will be used

University at Buffalo Institutional Review Board (UBIRB)

Office of Research Compliance | Clinical and Translational Research Center Room 5018
[name]
UB Federalwide Assurance ID#: FWA00008824

PROTOCOL TITLE: Effects of adrenocorticotropic hormone (Acthar gel®) on recovery from cognitive relapses in MS.

to compare the magnitude of change between day 0 and 90 between the MS patients treated with Acthar and the previously collected controls. Analysis of variance will also be used to compare the magnitude of cognitive recovery after corticosteroid treatment to that after Acthar treatment.

The difference between the means at Day 0 and Day 90 will be used to calculate Cohen's d for each group. To facilitate analysis, all data will be normalized using a large previously published control sample.¹³ All tests will be performed based on an alpha of 0.05. Net effect sizes removing estimated practice effects will be calculated using Cohen's d.

11.2 Provide a power analysis.

The selection of 30 as the target enrollment is based on the previously completed study of 25 relapsing and 25 stable MS patients. Five additional patients are planned in order to increase the power of subsequent analyses. A power analysis based on the observed effect of corticosteroids in the relapsing group of $d = .56$ with 30 participants will be powered $>85\%$ to detect effects of a moderate magnitude from Acthar.

11.3 Describe the steps that will be taken to secure the data (e.g., training, authorization of access, password protection, encryption, physical controls, certificates of confidentiality, and separation of identifiers and data) during storage, use, and transmission.

All clinical and neurometric assessments will be conducted under the supervision of the PI. All members of research team will complete relevant training programs and courses, including but not limited to: HIPAA, CITI and GRP.

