23.0 Local Number of Subjects

23.1 Indicate the total number of subjects to be accrued locally.

University at Buffalo Institutional Review Board (UBIRB)

Office of Research Compliance | Clinical and Translational Research Center Room 5018
[name]
UB Federalwide Assurance ID#: FWA00008824

PROTOCOL TITLE: Effects of adrenocorticotrophic hormone (Acthar gel®) on recovery from cognitive relapses in MS.

We will enroll 30 relapsing-remitting MS patients and 30 stable MS patients.

23.2 If applicable, distinguish between the number of subjects who are expected to be enrolled and screened, and the number of subjects needed to complete the research procedures (i.e., numbers of subjects excluding screen failures.)

During routine clinic appointments, cognitively relapsing patients will be assessed (by the treating clinician) for suitability for the study. Subjects who agree to participate and pass screening requirements will be enrolled in the study. Thirty relapsing MS patients and 30 stable MS controls will be enrolled.

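### Return to baseline is part of the primary hypothesis, but section 11.1 plans only difference tests: a non-significant day 90 difference could not confirm it, and no contrast, margin or confidence-interval rule is given

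*Combined protocol and SAP*

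**What the plan says.** Section 1.2 has two parts to the primary hypothesis: Acthar facilitates recovery, and "patients treated with Acthar will return to baseline following treatment".

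Section 11.1 lists these analyses, all at alpha 0.05:

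- A repeated-measures ANOVA: "Analysis strategy will be repeated measures analysis of variance where baseline, day 0 and day 90 scores are compared". Baseline is listed separately from day 0. No pairwise contrast is named.
- An ANOVA on the day 0 to day 90 change "between the MS patients treated with Acthar and the previously collected controls".
- An ANOVA to "compare the magnitude of cognitive recovery after corticosteroid treatment to that after Acthar treatment", with no time points named.
- An effect size: "The difference between the means at Day 0 and Day 90 will be used to calculate" Cohen's d in each group, plus net effect sizes with estimated practice effects removed.

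Scores are put on a common scale: "all data will be normalized using a large previously published control sample".

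Inclusion criteria 1a and 4 in section 3.1 tie the word baseline to earlier neuropsychological testing, which may be up to 4-5 years old. Section 9.2 uses the same word for the full battery given at day 0. Section 8.1 names four primary measures (SDMT, BVMT-R, PASAT and MSFC) and does not say on which of them return is to be judged.

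**The concern.** Showing that patients have returned to a former level is a claim of little or no remaining difference. A difference test does not supply that claim when it fails to reject. The omnibus ANOVA asks whether three means are equal. A drop at day 0 followed by full recovery can reject it, and so can a drop followed by partial recovery. Failure to reject does not show return either. The day 0 to day 90 analyses measure how far patients improved, not whether they got back to where they were.

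The return part of the primary hypothesis therefore has no rule by which it could be confirmed. The practical risk is a report with a significant day 0 to day 90 gain and a non-significant remaining deficit, in which partial recovery is described as return. The plan neither prescribes that reading nor rules it out.

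**Working it through.** **The plan's own figure.** Section 11.2 gives n = 30, d = 0.56 and power above 85%. As a within-group test, with d in units of the SD of change and alpha 0.05 two-sided, the noncentrality is 0.56 × √30 = 3.067. Power is 84.2% by noncentral t and 86.6% by the normal approximation, Φ(3.067 − 1.96). The stated figure thus agrees with a within-group test. As a comparison of two groups of 30 it would be 56.9% (t) or 58.3% (normal). Either way it is power to detect an effect, not to show return.

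**Precision of day 90 minus pre-relapse baseline.** n = 30 from sections 11.2 and 23.1. Two-sided testing is assumed, since the plan does not say. The half-width of the 95% interval is t(0.975; 29) / √30 = 2.045 / 5.477 = 0.373 SD of the difference.

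**How often a remaining deficit goes undetected.** Paired t test, noncentrality δ√30, with δ in SD of the difference. The original drop is assumed to be 0.56, borrowing only the size of d in section 11.2.

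| Share of drop remaining | δ | P(non-significant) |
|---|---|---|
| none (full return) | 0 | 95% |
| 25% | 0.14 | 88% |
| 50% | 0.28 | 68% |
| 75% | 0.42 | 40% |
| all | 0.56 | 16% |

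With half the assumed drop remaining, δ√30 = 1.534 and the test misses the deficit about two times in three.

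**Sensitivity to the correlation.** Suppose the deficit is instead 0.28 on the normalized score scale, with score SD taken as 1. The SD of the difference is √(2(1 − r)), where r is the assumed correlation between visits. The last two columns apply a rule that concludes return if the lower 95% limit is above minus 0.5 normalized SD. That margin is only an illustration.

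| r | SD of difference | P(0.28 deficit non-significant) | Rule met, full return | Rule met, 0.28 deficit |
|---|---|---|---|---|
| 0.3 | 1.183 | 76% | 61% | 16% |
| 0.5 | 1.000 | 68% | 75% | 21% |
| 0.7 | 0.775 | 52% | 93% | 32% |
| 0.8 | 0.632 | 35% | 99% | 45% |

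**After subtracting the controls' practice change.** The SD of change is assumed equal in both groups. The chance of meeting the 0.5 margin under full return falls to 36/48/69/85% for r = 0.3/0.5/0.7/0.8 with 30 controls, or 33/44/65/82% with 25. Both counts are shown because section 23.1 says "We will enroll 30 relapsing-remitting MS patients and 30 stable MS patients", whereas section 11.1 speaks of previously collected controls and section 11.2 of a "previously completed study of 25 relapsing and 25 stable MS patients".

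**The case against.** The pre-relapse baseline is not ignored. It is one of three levels in the main ANOVA, and pairwise comparison is an ordinary follow-up. A significant shortfall at day 90 would show that return is incomplete. On the figures above, a 0.28 score-SD deficit would be detected in 24% to 65% of trials. A reader might infer that the planned tests cannot tell full from partial return at all. That goes too far: they can refute return but not confirm it.

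A reader might also infer that the investigators intend to treat p > 0.05 as return. Nothing in the documents says so, and the harm depends on that reading. This is also an open-label study with a stable control group, not a formal equivalence trial, so how strict the criterion should be is partly a matter of judgement.

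The objections to the figures stand as well. The SD of 1, the correlations, the drop and the margin are all assumed. Normalizing to an external sample does not make the SD 1 in these patients. The type of d in section 11.2 is not defined, and SD-of-change units equal score-SD units only at r = 0.5. Selection on SDMT decline from the same baseline (section 3.1) is not modelled.

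Lastly, a margin is not a cure by itself. A margin of 0.5 SD treats a 0.28 deficit as acceptable, and at r = 0.8 it would pass that deficit 45% of the time, more often than the 35% non-significance rate.

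These points limit the size of the claim. They do not supply the missing contrast or rule.

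**Conclusion.** The point holds in this form: return to baseline is in the primary hypothesis, and the plan contains no analysis that could confirm it. That follows from reading sections 1.2 and 11.1 together and needs no numerical assumption. The documents support neither a claim that the baseline is left out nor a claim that non-significance will be read as return.

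The size is illustrative. With 30 patients the interval half-width is about 0.37 SD of the difference, and a deficit of 0.28 SD of the difference would be non-significant about 68% of the time. If 0.28 is read on the score scale, the figure runs from 76% to 35% as the assumed correlation rises from 0.3 to 0.8.

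The plan should be changed, but the defect is not fatal: improvement from day 0 to day 90 remains testable and the repair is cheap.

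**What to change.** In section 11.1:

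1. Define baseline as the pre-relapse neuropsychological score of inclusion criterion 4, and use a different term for the day 0 battery in section 9.2.
2. For each primary measure that has a pre-relapse score, report day 90 minus that score (higher meaning better) with its two-sided 95% confidence interval. List the measures.
3. State that p > 0.05 is not evidence of return. Conclude return only if the lower limit lies above minus a margin that is justified and fixed before analysis. Otherwise report recovery as incomplete if the upper limit is below zero, and as inconclusive if it is not. No margin can be derived from the documents; the 0.5 used here is not a recommendation.
4. Keep the day 0 to day 90 contrast for improvement.
5. Give a practice-adjusted version as a partial sensitivity analysis only, and state how many controls it uses. The controls' practice change covers three months, while the pre-relapse score may be 4-5 years old.

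The cost is SAP wording and a margin justification, with no new visits. The downside is that the return conclusion may be inconclusive even when return is complete. At an assumed margin of 0.5 SD and correlation of 0.5, success is about 75%, falling to 48% with 30 controls or 44% with 25 after practice correction. In units of the SD of the difference, a tighter margin costs more: at 0.4 success under full return is about 56%, and at 0.3 about 36%.

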3.0 Inclusion and Exclusion Criteria

3.1 Describe the criteria that define who will be included or excluded in your final study sample.

Inclusion Criteria:

- (1) Identification by clinical care provider of new acute (defined by clinician as a symptom of recent origin developing with a time span of 48 hours) cognitive relapse or supratentorial GAD enhancing lesions on MRI with confirmation of cognitive decline.
 - (1a) Confirmation of cognitive decline will be obtained by administering the SDMT as a screening procedure for the study. Participants will qualify if they show a > -3 raw score point change on SDMT (relative to baseline identified to meet criteria #4).
- (2) Males/Females between the ages of 18-65 years who are capable of understanding and complying with the protocol, speak and write fluent English, and have at least a 9th grade education.
- (3) Have a diagnosis of Relapsing Remitting or early Secondary Progressive MS as per revised McDonald's Criteria.
- (4) Valid NP testing in the past 4-5 years
- (5) EDSS of ≤ 7.0
- (6) Have given written informed consent prior to any study-related procedure not part of normal medical care, with the understanding that consent may be withdrawn by the subject at any time without prejudice to his/her future medical care.
- (7) Are capable of performing the requirements of a NP test battery including at least 20/70 near visual acuity by near vision chart, with correction.

Exclusion Criteria:

- (1) Have cognitive deficits caused by concomitant medication usage or other significant neurological/psychological disease e.g. Alzheimer's disease, Parkinson's disease, stroke, transient ischemic attack, Vascular Dementia, Huntington's disease, traumatic brain injury, or chronic CNS infection.
- (2) Have evidence of any other medical cause(s) of cognitive impairment.

University at Buffalo Institutional Review Board (UBIRB)

Office of Research Compliance | Clinical and Translational Research Center Room 5018
[name]
UB Federalwide Assurance ID#: FWA00008824

PROTOCOL TITLE: Effects of adrenocorticotropic hormone (Acthar gel®) on recovery from cognitive relapses in MS.

- (3) Have evidence of current major depression as determined by a positive BDI-FS and clinician interview.
- (4) Clear new physical signs or symptoms that are referable to the spinal cord, brainstem, or optic nerve.
- (5) Evidence on MRI of new lesions in the brainstem, spinal cord, or optic nerve.

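### The return-to-baseline hypothesis rests on a contrast for which section 11.1 names no control group, so practice since the pre-relapse test is left uncorrected

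*Combined protocol and SAP*

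**What the plan says.** The primary hypothesis in section 1.2 has two limbs: Acthar facilitates recovery, and "patients treated with Acthar will return to baseline following treatment". Section 1.1 gives the reason for the stable group: "To account for the possible practice effects of cognitive testing over a three-month period".

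Section 11.1 then lists these analyses:

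- "Analysis strategy will be repeated measures analysis of variance where baseline, day 0 and day 90 scores are compared". No group factor is named.
- Analysis of variance "to compare the magnitude of change between day 0 and 90 between the MS patients treated with Acthar and the previously collected controls".
- "The difference between the means at Day 0 and Day 90 will be used to calculate Cohen's d for each group".
- "Net effect sizes removing estimated practice effects will be calculated using Cohen's d". No version of this net effect size using the pre-relapse score is given.

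The pre-relapse score comes from entry criterion 4 in section 3.1: "Valid NP testing in the past 4-5 years". Section 9.6 has study data collected at months 0 and 3. No earlier test is described for the controls, whom section 11.1 treats as already collected and sections 23.1 and 23.2 say will be enrolled (30 patients).

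**The concern.** The return limb needs day 90 compared with the pre-relapse test. That is a different contrast from the day 0 to day 90 change, and it spans more test exposures. Before day 90 a relapsing patient has taken the SDMT at the pre-relapse test, at screening (section 9.2, described for the relapsing patient only) and again in the day 0 battery. None of these exposures precedes the pre-relapse score.

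The plan treats practice as a bias worth correcting, but every stated correction stops at the day 0 to day 90 window. Practice raises day 90 relative to the pre-relapse score. Part of an apparent return could then be practice credited to Acthar, on a stated limb of the primary hypothesis in an open-label, non-randomised study.

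**Working it through.** **The plan's own power figure.** Section 11.2 states more than 85% with d = 0.56 and 30 participants. For a one-group paired test at two-sided alpha 0.05 (sidedness is not stated), the normal approximation gives Φ(0.56 × √30 − 1.96) = Φ(1.107) = 86.6%; the exact t gives 84.2%. For 30 against 30 the exact t gives 56.9%. The figure therefore fits a within-group change. It comes from the corticosteroid effect and is not a calculation for return to baseline.

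**What each contrast estimates.** Let L be the true loss at relapse, R the true recovery by day 90, P1 the practice present by day 0, P2 the practice added from day 0 to day 90, and A any drift from ageing or disease since the earlier test. For simplicity, A accrues before day 0. The expected changes are:

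- Acthar, day 90 minus day 0: R + P2.
- Controls, day 90 minus day 0: P2, if their practice is equal.
- The difference is R. The planned controlled comparison isolates recovery.
- Acthar, day 90 minus pre-relapse: −L + R + P1 + P2 + A.

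Return means R = L, but the last line equals zero whenever R + P1 + P2 + A = L. For illustration, take L = 4, R = 2, P1 + P2 = 2 and A = 0: the expected difference is zero while a 2-point loss remains. Controls with an earlier test over a similar interval would estimate P1 + P2 + A. Section 11.1 does not provide for this.

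**How often a shortfall would be missed.** Inputs: n = 30 from the protocol; SD of change and remaining deficit assumed, since the documents give neither. Method: two-sided paired t with noncentrality (deficit / SD) × √30. At SD 5 a deficit of 4 gives 0.8 × 5.477 = 4.38. The table shows the chance that day 90 is not significantly below baseline.

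| Remaining observed deficit | SD 5 | SD 6 | SD 8 |
|---|---|---|---|
| 4 points | 1% | 6% | 25% |
| 2 points | 44% | 58% | 74% |
| 1 point | 81% | 86% | 90% |

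Equivalently, an observed deficit below 2.045 / √30 = 0.37 SD of change is non-significant.

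**With and without controls.** This is a simulation of 4,000 runs with 30 per group, an assumed true deficit of 6, no recovery and error SD 4 per test (change SD 4 × √2 = 5.7). With total practice of 0, 2, 4 or 6 points, the Acthar group alone shows no significant difference from baseline in 0.0%, 3.7%, 53.1% or 94.6% of runs. With controls tested at the same three times and having equal practice, the figure stays at 1.7% to 2.0%. The planned day 0 to day 90 comparison with controls gives about 5% false positives throughout.

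**The case against.** **Section 11.1 does not exclude the controls.** A reader might infer that the three-time-point ANOVA is fixed as single-group. The text names no group, so that is not established. But it does not include the controls either, and no earlier control test is described that could fill the first time point.

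**With no recovery at all, the controlled comparison would expose a false return.** An observed day 0 deficit could then close only through practice after day 0, and the comparison with controls would show no net gain. This is a real partial safeguard. It fails when recovery is real but incomplete, as in the L = 4, R = 2 example, and the plan does not make the return claim conditional on it.

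**Practice per exposure cannot simply be multiplied by three SDMT exposures.** A reader might be tempted to do so. Entry depends on an observed decline ("Participants will qualify if they show a > -3 raw score point change on SDMT"), and that screening score already contains practice retained from the pre-relapse test. Subtracting the practice again from the observed loss would count it twice. The table is therefore stated in remaining observed deficit, with no practice gain per exposure.

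**The direction is not certain.** The earlier test may be 4 to 5 years old, and ageing or disease change (A below zero) would lower day 90 against it. This stands: a net bias in favour of Acthar cannot be asserted. It is also a reason to have a control contrast over a similar interval.

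**Not every measure is known to be affected.** Criterion 4 does not list the tests in the earlier evaluation. Criterion 1a shows that a baseline SDMT is needed. Prior BVMT-R and PASAT exposure is plausible but not stated.

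**Conclusion.** As written, the return-to-baseline limb is tested by a contrast with no stated practice correction, while the recovery limb has one. An apparent return can therefore be partly practice, including practice from the extra screening SDMT.

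The size cannot be fixed from the documents. The miss rates of about 1%, 44% and 81% rest on an assumed SD of 5 and assumed remaining deficits of 4, 2 and 1 points; a larger SD raises all three. A reader might infer that practice alone would produce a full return without any recovery. That requires practice, net of any decline from ageing or disease, to be about as large as the loss, and the documents give no practice estimate to support it. They also state no margin for return, so a non-significant difference would not demonstrate it even with practice removed.

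**What to change.** In section 11.1:

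1. Reconcile the description of the controls as already collected with the statement in sections 23.1 and 23.2 that 30 will be enrolled. This decides whether an earlier test can be required of them or only looked for in existing records.
2. Where controls have an earlier neuropsychological test on file, fit the three-time-point model with both groups and a group-by-time term. Report return as (Acthar day 90 minus pre-relapse) minus (control day 90 minus earlier test), with a confidence interval judged against a margin stated in advance, not by non-significance.
3. If controls have no earlier test, make no return-to-baseline claim from the single-group contrast. Rest the conclusion on the controlled day 0 to day 90 change.
4. State that the screening SDMT is described only for relapsing patients, so that exposure is not matched in controls and the correction for the SDMT is incomplete.

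The cost is analysis wording and a records check. Precision falls. With deficit 4, SD 5 in both groups and 30 per group, the two-group noncentrality is 0.8 / √(2/30) = 3.10, and power is about 0.86 against 0.99 for one group. The 95% half-width grows from 2.045 × 5 / √30 = 1.87 to 2.002 × 5 × √(2/30) = 2.58 points. Controls without an earlier test cannot be used for this contrast, which would widen the interval further.

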8.0 Study Endpoints

8.1 *Describe the primary and secondary study endpoints.*

Primary measures will include: Symbol Digit Modalities Test,¹⁴ Brief Visualspatial Memory Test- Revised,¹⁵ Paced Auditory Serial Addition Test,¹⁶ and the Multiple Sclerosis Functional Composite (MSFC).²³ These tests are some of the strongest indicators of clinically relevant cognitive change available in MS.

The Symbol Digit Modalities Test (SDMT) will be used to measure visual processing speed. This test presents a stimulus key of numbers paired with abstract symbols at the top of a page. Participants scan the page below the key which has rows of symbols without the paired numbers. The task is to generate the associated numbers orally as fast as possible. We will employ the Rao oral adaptation²⁴ of the SDMT as the oral presentation has been deemed most appropriate for use with a potentially motor impaired population.¹²

University at Buffalo Institutional Review Board (UBIRB)

Office of Research Compliance | Clinical and Translational Research Center Room 5018
[name]
UB Federalwide Assurance ID#: FWA00008824

PROTOCOL TITLE: Effects of adrenocorticotropic hormone (Acthar gel®) on recovery from cognitive relapses in MS.

The Paced Auditory Serial Addition Test (PASAT)²⁵ 3 sec interval version will be used as an indicator of working memory performance. The PASAT is an auditory task in which subjects are exposed to single digit numbers voiced every three seconds. After each number presentation, the subject's task is to respond with the sum of the last two digits presented. As each new number is presented, the subject must recall the previous digit, add them together, and respond before the next number is presented.

The Multiple Sclerosis Functional Composite (MSFC)²³ is a composite measure incorporating aspects of cognition, walking speed and manual dexterity. The 25-foot walk, 9-hole peg test, and PASAT 3-sec (described above) are normalized based on an established normative sample and an overall composite z- score is then determined. This composite is frequently used as a primary outcome in clinical trials as it covers three major domains of function potentially impaired in MS.

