The Brief Visuospatial Memory Test Revised (BVMTR)^{26,27} is a measure of episodic memory. This task presents a display of six visual designs presented on an 8.5 x 11 piece of paper for three consecutive learning trials. During each trial the stimulus is presented for 10 seconds, after which the participant is asked to draw the figures as accurately as possible in their correct locations. The six designs receive a score of 0, 1, or 2 based on accuracy and location. After a 20-25 minute delay, participants are again asked to recall and draw the designs.

The North American Adult Reading Test (NAART) is a measure of verbal ability. Patients are asked to read a list of words aloud.

Secondary measures will include: self and informant ratings of cognitive problems using the Multiple Sclerosis Neuropsychological Questionnaire,²⁸ the Expanded Disability Status Scale,²⁹ the Multiple Sclerosis Impact Scale, the Beck Depression Inventory – Fast Screen, and subscales from the Sickness Impact Profile³⁰ (an assessment of health related quality of life and activities of daily living). Incidence of adverse events and concurrent medications will also be recorded as potential covariates.

8.2 Describe any primary or secondary safety endpoints.

N/A

[figure not shown]

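### Four unranked primary measures are each tested at 0.05, with no testing order, multiplicity rule or success rule, and neither the primary hypothesis nor the power statement names a measure.

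*Combined protocol and SAP*

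**What the plan says.** Section 8.1 opens its endpoint list with "Primary measures will include: Symbol Digit Modalities Test" and adds BVMT-R, PASAT and MSFC in the same sentence, without order or weight. Two of the four overlap, because MSFC is built from PASAT: "The 25-foot walk, 9-hole peg test, and PASAT 3-sec (described above) are normalized based on an established normative sample". BVMT-R yields three learning trials and a later recall ("After a 20-25 minute delay, participants are again asked to recall and draw the designs"), and no score is named as the endpoint.

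Section 11.1 describes three analyses. The first covers three time points: "Analysis strategy will be repeated measures analysis of variance where baseline, day 0 and day 90 scores are compared". The second sets the day 0-90 change in Acthar patients against that in stable controls whose data were gathered earlier. The third does the same for recovery after corticosteroids against recovery after Acthar. The section then sets one rule for significance: "All tests will be performed based on an alpha of 0.05".

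Section 1.2 states a single primary hypothesis with two parts: that Acthar aids recovery, and that "patients treated with Acthar will return to baseline following treatment". It attaches no measure, criterion or test to either part. Sections 1.1 and 7.1 name stable MS patients as the comparison but no measure. Section 11.2 gives d=.56 and power above 85% with 30 participants, and names neither the measure nor the comparison.

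**The concern.** With four primary measures each tested at 0.05 and no success rule, the 0.05 in 11.1 is an error rate per test and not for the primary claim. The plan does not say whether one, some or all of the four must succeed. A single nominal p<.05 could therefore be presented as a primary finding, and nothing in the text would rule that out.

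The unspecified BVMT-R score adds a further choice that could be made after the results are seen. The missing link between 1.2 and a test adds another, because the two parts of the hypothesis call for different analyses.

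**Working it through.** **Inputs from the documents.** Four primary measures, with PASAT a component of MSFC (8.1); alpha 0.05 for every test (11.1); d=.56, 30 participants, power >85% (11.2); 30 relapsing and 30 stable patients (23.1, 23.2). The controls are also called previously collected (11.1), and the earlier study had 25 stable patients (11.2). Sidedness is not stated; two-sided is assumed.

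**Step 1: the plan's own power figure.** Take d=.56 in SD units of the day 0-90 change, within one group of 30.
- Normal approximation: Φ(d√n − 1.960) = Φ(.56 × 5.477 − 1.960) = Φ(1.107) = 87%.
- Exact noncentral t, 29 df, noncentrality .56√30 = 3.07: 84%.

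So >85% is reproduced, to within a point on the exact test, as a within-group test on one measure at an unadjusted 0.05.

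**Step 2: chance of at least one false positive, four measures, Acthar versus stable controls.** If the tests were independent, 1 − .95⁴ = 18.5%. They are not, so the null was simulated. Five equicorrelated change scores (SDMT, BVMT-R, PASAT, walk, peg test) were drawn, with MSFC as the mean of the last three. Groups were 30 versus 30, with two-sample t-tests and 100,000 trials per correlation.

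| Assumed correlation | Any of four at p<.05 | Holm over four (smallest p<.0125) |
|---|---|---|
| 0 | 17.7% | 4.9% |
| .3 | 16.0% | 4.4% |
| .5 | 14.4% | 4.1% |
| .7 | 12.1% | 3.3% |

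With 25 controls the any-of-four range is 17.8% to 12.1%. A single named measure tested first at 0.05 gives 4.8-5.1%. The documents give no correlations, so these are ranges under an assumption.

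**Step 3: power under the alternatives.** Holm's strictest step is .05/4 = .0125. Take d=.56 in change-score SD units and no change in controls. The two-group noncentrality is d√(n₁n₂/(n₁+n₂)): .56√15 = 2.17 for 30 v 30, and .56√(750/55) = 2.07 for 30 v 25.

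| Analysis (exact t) | alpha .05 | alpha .0125 |
|---|---|---|
| Within-group, n=30 | 84% | 66% |
| 30 v 30 controls | 57% | 35% |
| 30 v 25 controls | 53% | 31% |

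**Step 4: sensitivity to the standardiser, which 11.2 does not state.** If d=.56 is in score SD units, the change-score effect is .56/√(2(1−r)) for test-retest correlation r. For assumed r of .3, .5, .7 and .8, power for 30 v 30 at .05 is 44%, 57%, 79% and 92%; at .0125 it is 24%, 35%, 59% and 80%. An assumed practice gain of 0.1 score SD in controls lowers the .05 figures to 32%, 42%, 62% and 79%.

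**Step 5: which analysis answers 1.2.** Day 0-90 change against stable controls addresses recovery net of practice effects, the role that 1.1 gives the controls. It does not use the pre-relapse score, so it cannot show a return to baseline. Only the repeated-measures analysis includes that score, and 11.1 gives no criterion for return. A non-significant difference between baseline and day 90 would not supply one.

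**The case against.** The strongest reply is that multiplicity is a lesser threat here. This is a 30-patient, open-label, non-randomised study that also reports effect sizes and practice-adjusted net effects. Relapsing patients selected for an SDMT decline may improve more than stable patients with no help from the drug. If that excess were 0.3 change-score SD (assumed), a single measure at 0.05 would be significant in 21% of 30 v 30 studies; at 0.5 SD, in 48%. This stands. It limits what the fix can achieve, but it does not excuse leaving the primary claim undefined.

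A reader might infer several stronger points that the documents do not support:
- That the plan declares success if any one measure is significant. It states no success rule at all; the fault is the silence.
- That the error rate is 21-30%, by adding the corticosteroid comparison as a route to primary success. Section 11.1 brings that comparison in as an additional analysis, and 1.1, 1.2 and 7.1 do not mention it, although the background lists it as an aim.
- That the information processing speed composite in 9.2 is a further primary endpoint. It is not listed in 8.1.
- That the comparison with controls is by itself the test of 1.2. It leaves out the pre-relapse baseline.
- That about 5% after the fix is the risk of a false claim about Acthar. It is the error rate for a group difference.

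**Conclusion.** The point holds and should be corrected, though it is not the main threat to validity in this design. As written, the chance of at least one false positive across the four primary measures in the control comparison is about 12-18%, more than twice the stated 0.05. This assumes two-sided tests, equal expected change in the two groups under the null, and correlations between 0 and .7. Naming one measure brings the rate to about 5%, and Holm to about 3-5%.

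With d=.56 read as change-score SD units, the power in 11.2 belongs to a within-group test and leaves no room for adjustment. On that reading it does not carry over to the comparison with controls. If d is in score SD units, power for that comparison runs from 44% to 92% over the assumed test-retest correlations, so the standardiser has to be stated.

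**What to change.** Amend 8.1 and 11.1 before Acthar outcome data are examined. The controls and the earlier corticosteroid data are already in hand, so blindness to all data is not attainable.

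1. Name one primary measure with its exact score, and one primary analysis, tested at two-sided 0.05.
2. Test the other three measures in that analysis by fixed sequence or Holm only if the first succeeds. Alternatively, apply Holm across all four.
3. Label all other analyses, including the corticosteroid comparison, secondary or exploratory.
4. State which part of 1.2 the chosen analysis tests. If return to baseline is claimed, use the pre-relapse score and set a criterion for return in advance.
5. If SDMT is chosen, take the second day 0 administration (9.2) as the starting value. The screening score decides entry, so using it would build in regression to the mean.

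The cost is wording and a restated power figure in 11.2. That figure should name the analysis, the standardiser for d, the assumed change in controls and the actual number of controls, with 11.1, 11.2 and 23.1 reconciled on that number. A named first measure keeps the full 0.05. Holm across all four lowers power at its strictest step from 84% to 66% within-group, and from 57% to 35% (30 controls) or 53% to 31% (25 controls) for the control comparison, on the change-score reading of d. The report should also say that multiplicity control does not separate a drug effect from natural recovery.
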